#### **Control Group:**

Patients are given verbal information about the procedure. Then:

- VAS test is applied.
- STAI-II (Trait Anxiety) and STAI-I (State Anxiety) scales are administered pre-procedure.
- After biopsy: VAS and STAI-I are re-administered.
- No visual material is shown.

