#### **Video Group:**

Patients are given verbal information. Then:

- VAS test is applied.
- Videos about the procedure are found and watched with the patients via digital video platforms.
- STAI-II and STAI-I are administered pre-procedure.
- After biopsy: VAS and STAI-I are re-administered.

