## **7. Sample Size:**

No similar study was found in the literature. There are three independent groups:

- Video group,
- No visual group,
- Image group.
- Assuming an alpha ( $\alpha$ ) level of 0.05 and a beta ( $\beta$ ) level of 0.20 (power of 80%), and an effect size (Cohen's  $f$ ) of 0.40, it was calculated that approximately 26 participants per group (78 in total) would be required to detect meaningful differences between the three groups.

---

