## **10. Withdrawal Criteria:**

- Participants may withdraw at any time.
- Patients who become excessively anxious or restless during biopsy will have the procedure rescheduled under general anesthesia and be excluded from the study.

---

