## **17. Outcome Evaluation:**

The primary endpoint is the tabulation and statistical analysis of STAI responses before and after the procedure among different groups. The secondary endpoint is the writing and publication of the study results.

---

Previous literature has shown that prostate biopsy induces anxiety and depression. Zisman et al., in a prospective study of 211 men, found that 64% experienced decreased well-being and anxiety from the pre-biopsy period up to 30 days after. Fowler et al. showed that anxiety may persist for up to 12 months, even in patients with negative biopsy results. Our study seeks to answer whether pre-procedural videos intensify the anxiety already known to be associated with the biopsy.

---

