### **Name / Signature**

**Principal Investigator:**  
**[name]**

### **Statistical Analysis**

All statistical analyses were performed using SPSS software [insert version]. Continuous variables were expressed as mean  $\pm$  standard deviation, and categorical data as frequencies and percentages. Group comparisons were made using the Kruskal-Wallis test for non-parametric data and ANOVA for normally distributed data. Post-hoc pairwise comparisons were conducted using the Mann-Whitney U test with Bonferroni correction. A p-value  $<0.05$  was considered statistically significant. A priori power analysis was conducted using G\*Power

software version 3.1.9.7 to determine the adequate sample size. Assuming an alpha ( $\alpha$ ) level of 0.05 and a beta ( $\beta$ ) level of 0.20 (power of 80%), and an effect size (Cohen's  $f$ ) of 0.40, it was calculated that approximately 26 participants per group (78 in total) would be required to detect meaningful differences between the three groups.

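### Cheap improvement, not an error: with three groups, testing pairs at 0.05 only after a significant overall test could replace Bonferroni and recover power on the video question

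*Combined protocol and SAP*

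**What the plan says.** In the final Statistical Analysis section the overall test depends on the distribution: "Group comparisons were made using the Kruskal-Wallis test for non-parametric data and ANOVA for normally distributed data". The pairwise step follows without any condition: "Post-hoc pairwise comparisons were conducted using the Mann-Whitney U test with Bonferroni correction". No other pairwise test is named there, so on its natural reading Mann-Whitney follows ANOVA as well as Kruskal-Wallis. The section does not give the Bonferroni factor. It also does not say that pairs are tested only when the overall test is significant; the term post-hoc suggests this but does not state it. Section 18 lists the t-test and Mann-Whitney among many methods and ties neither to a comparison.

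Section 7, repeated in the final section, sizes the study for the three-group comparison at alpha 0.05, 80% power and Cohen's f = 0.40: "approximately 26 participants per group (78 in total) would be required to detect meaningful differences between the three groups".

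Section 17 puts the research question as a statement about one group: "Our study seeks to answer whether pre-procedural videos intensify the anxiety already known to be associated with the biopsy". It defines the outcome broadly: "The primary endpoint is the tabulation and statistical analysis of STAI responses before and after the procedure among different groups". No single STAI score or time point is singled out.

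**The concern.** The sample size is set for the overall test, but the question in section 17 needs a comparison involving the video group, read here as video against verbal information only. The overall test cannot say which groups differ or in which direction.

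Dividing alpha by three for that comparison gives up power. With exactly three groups the division is not needed, provided that the pairs are tested only after a significant overall test. What is at stake is avoidable loss of power on the study's own question, not a false positive rate that is too high.

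**Working it through.** **Inputs from the documents** (section 7 and the final section): three groups, 26 each, alpha 0.05, power 80%, f = 0.40. **Assumed, because not stated:** two-sided pairwise tests, Bonferroni factor 3 (0.05/3 = 0.0167), one STAI score analysed at one time point, normal data with equal SDs unless noted.

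**1. The plan's own figure.** One-way ANOVA, noncentral F with λ = N·f².
- N = 66: λ = 66 × 0.16 = 10.56, power 81.8%. So 66 (22 per group) is enough for 80%.
- N = 78: λ = 78 × 0.16 = 12.48, power 88.3%.

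The stated 78 is not reproduced from the stated inputs. It would follow from, for example, 15% dropout (66/0.85 = 77.6), which the plan does not mention. The overall test is therefore not short of power, and this mismatch does not affect the present point.

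**2. From f to the video-control difference d (in SDs).** The documents do not say where the means fall, so three patterns are used.
- Image equals control: f = d·√2/3, so d = 0.40 × 3/√2 = 0.85.
- Image midway between control and video: f = d/√6, so d = 0.40 × √6 = 0.98.
- Control midway between video and image: d = 0.98/2 = 0.49.

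**3. Familywise error of the omnibus-first rule.** If all three groups are equal, the overall test at 0.05 limits the error. If exactly one pair is equal, only one true null remains and it is tested at 0.05. If no pair is equal, no false rejection is possible. This is a closed test, and the argument does not carry over to four or more groups. Simulated error with all groups equal:
- as written (ANOVA, then Bonferroni Mann-Whitney): 3.3%
- omnibus-first, Welch: 5.0%
- omnibus-first, ranks: 4.9%
- Welch tests at 0.05 with no overall test first: 12.2%

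**4. Power for video against control** (40,000 simulated trials per pattern, in %):

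| Pattern | ANOVA, Mann-Whitney at 0.05/3 (as written) | Welch ANOVA, Welch at 0.05/3 | Welch ANOVA, Welch at 0.05 | Kruskal-Wallis, Mann-Whitney at 0.05 |
|---|---|---|---|---|
| Image equals control | 68.5 | 71.5 | 81.3 | 79.3 |
| Image midway | 82.0 | 84.9 | 87.4 | 86.0 |
| Control midway | 23.2 | 24.8 | 40.5 | 38.3 |

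Reading the plan with or without an overall test first hardly changes the as-written column (69.0, 82.9 and 23.2 without).

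**5. Where the gain comes from.**
- Moving from Mann-Whitney to Welch tests: 71.5 − 68.5 = 3.0; 84.9 − 82.0 = 2.9; 24.8 − 23.2 = 1.6 points.
- Dropping Bonferroni: 81.3 − 71.5 = 9.8; 87.4 − 84.9 = 2.5; 40.5 − 24.8 = 15.7 points.

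Bonferroni is the larger part except when image is midway, where both parts are small and about equal. The rank route keeps Mann-Whitney throughout and still gains: from 68.7, 82.4 and 23.2 at 0.05/3 to 79.3, 86.0 and 38.3 at 0.05.

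**6. Sensitivity.**
- Skewed scores (assumed skewness 1): Kruskal-Wallis then Bonferroni Mann-Whitney gives 77%, 88% and 29%. Kruskal-Wallis then Mann-Whitney at 0.05 gives 86%, 91% and 45%. Welch gives 82%, 87% and 41%, so it gains nothing there when image is midway.
- Unequal SDs (assumed ratios 1.5 and 2, one group far apart): the remaining true null is rejected in about 5% of trials with Welch, 5-6% with Mann-Whitney, and 7-9% with pooled-variance contrasts.

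**The case against.** The strongest reply is that this is a choice between legitimate methods. Bonferroni-corrected Mann-Whitney tests hold the error rate with or without a preceding overall test, and they need neither normality nor equal SDs. The omnibus-first rule is safe only if it is written down, and it gives up simultaneous intervals: at least one of three ordinary 95% intervals misses in about 12% of trials. All of this stands, and it is why the point is an improvement and not a defect.

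A second reply is that, if video against verbal information is the question, that contrast could be the single primary test at 0.05, with neither Bonferroni nor an overall test. On normal data this gives about 85%, 94% and 41% by Welch. It is a fair alternative, but section 17 defines the endpoint across the groups and names no single contrast, so it would change the stated aim more than the rule proposed here.

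A third is timing. The final section is in the past tense, recruitment was to end on 30.12.2024 (section 14) and the study on 20.05.2025 (section 15). The documents do not say whether group results have been seen. If they have, most of the benefit is gone.

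Three stronger readings are tempting, and the material does not support them:
- A reader might infer that using Mann-Whitney after ANOVA is the main fault, because a significant ANOVA can then end with no significant pair. On normal data that happens in about 6% of significant ANOVAs as written, about 3% with Bonferroni-corrected Welch tests, and 0.3% with Mann-Whitney at 0.05. Bonferroni is the larger cause.
- A reader might infer that the study has only 23% power for its question. That figure needs control to lie exactly midway (or video midway between the other two), which no document suggests. With the video-control difference fixed at an assumed 0.80 SD, power as written is 62-63% in all three patterns.
- A reader might infer that adjusting for STAI-II would add power at no cost. In the control group, "STAI-II (Trait Anxiety) and STAI-I (State Anxiety) scales are administered pre-procedure" with no visual material involved. In the video group, the step "Videos about the procedure are found and watched with the patients via digital video platforms" is listed before STAI-II, and the image group likewise lists the drawings first. STAI-II may therefore be affected by the exposure, and adjustment could remove part of the effect. It forms no part of the recommendation.

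**Conclusion.** The plan's pairwise step is valid but conservative. With three groups and one named outcome, an omnibus-first rule keeps familywise error at about 5%. It raises power for video against verbal information from about 68% to 79-81% if only video differs, and from 82% to 86-87% if image is midway. If control is midway, power rises from about 23% to 38-40%, so the rule does not always reach 80%.

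These figures rest on f = 0.40, 26 analysed per group, two-sided tests, a Bonferroni factor of 3 and normal data. They ignore any before-after modelling.

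Valid here refers to multiplicity only. The documents state no allocation method, and section 10 says: "Patients who become excessively anxious or restless during biopsy will have the procedure rescheduled under general anesthesia and be excluded from the study". Whether the groups are comparable is a separate matter, which neither pairwise rule settles.

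**What to change.** 1. Name one STAI-I score at one time point as the primary outcome.
2. State in the SAP that the overall group effect is tested at 0.05 and that the three pairwise tests, each at 0.05, are run only if it is significant.
3. Fix one matching route in advance: Welch ANOVA then Welch contrasts, or Kruskal-Wallis then Mann-Whitney. The rank route is the better choice if scores are expected to be skewed. Avoid pooled-variance contrasts unless equal SDs can be defended.
4. Label all other STAI time points and VAS as secondary, and do not extend the 5% claim to them.
5. If Welch intervals are reported, say that they are not simultaneous.
6. If group results are already known, keep the Bonferroni analysis as planned, state its factor, and report the omnibus-first contrasts as secondary.

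The cost is SAP wording, with no new data or patients. The price is that error control covers only the named outcome and the three intervals do not hold jointly at 95%.

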**1. Full Title of the Study:**

**"A Prospective Comparative Study of the Effect of Video Education on Pain and Anxiety in Patients Undergoing TRUS-Guided Prostate Biopsy"**

---

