## **11. Parameters to be Measured:**

- Age
- PSA levels
- Subjective findings of rectal examination
- Post-procedure complications
- Anxiety and stress scores (STAI-I and II, pre-op and post-op)
- Pain scores (VAS)

---

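### No error control across the anxiety and pain outcomes: Bonferroni is attached only to post-hoc group pairs, and no single STAI score is primary

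*Combined protocol and SAP*

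**What the plan says.** The title announces two effects: "Effect of Video Education on Pain and Anxiety". Section 4 (Study Design) has STAI-I given before and after the biopsy in every group, and VAS repeated after the biopsy. STAI-II, the trait scale, is given once, before the procedure. Section 11 is looser: "Anxiety and stress scores (STAI-I and II, pre-op and post-op".

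Section 17 (Outcome Evaluation) states: "The primary endpoint is the tabulation and statistical analysis of STAI responses before and after the procedure among different groups". It picks no score and no time point. Its secondary endpoint is publication, so pain has no place in the ranking.

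The final Statistical Analysis section gives the decision rules:

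- Omnibus step: "Group comparisons were made using the Kruskal-Wallis test for non-parametric data and ANOVA for normally distributed data".
- Pairwise step: "Post-hoc pairwise comparisons were conducted using the Mann-Whitney U test with Bonferroni correction".
- Threshold: "A p-value $<0.05$ was considered statistically significant".

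No section gives an order of testing, an alpha split or an exploratory label across outcomes.

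**The concern.** With three groups there are three pairs per outcome, and the natural reading of the Bonferroni step is that it covers those three pairs. On that reading each outcome has its own 5% allowance. Three outcomes can respond to the material shown: pre-procedure STAI-I, post-procedure STAI-I and post-biopsy VAS. Two of them fall inside the primary endpoint as written, so the multiplicity exists before pain is counted.

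At stake is how a single significant score among several could be reported. The plan does not say which result would confirm an effect and which would only support it, so the choice could be made after the results are seen. The pairwise correction does not address this, because it works within an outcome and not across outcomes.

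**Working it through.** **Inputs from the documents.** Three groups (section 7: "There are three independent groups"); 26 per group, 78 in total; alpha 0.05; power 80%; Cohen's f 0.40; Bonferroni on pairs.

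**Assumptions, because the documents are silent.** Two outcomes (one STAI-I score and VAS) or three (both STAI-I time points and VAS); equal correlation between outcomes, 0 to 0.8; Bonferroni over three pairs, so 0.05/3 = 0.0167 per pair.

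**The plan's own figure.** One-way ANOVA with noncentrality f² × N reaches 80% power at N = 66 (22 per group, 81.8%). At N = 78, noncentrality is 0.16 × 78 = 12.48 and power is 88.3%. So 78 is not the minimum for the stated inputs. That is a separate matter, but the margin is relevant to the fix. The documents state no familywise rate to reproduce.

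**Independent outcomes, closed form.** Chance of at least one false omnibus result = 1 − (1 − 0.05)^k.

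- k = 2: 1 − 0.95² = 9.75%
- k = 3: 1 − 0.95³ = 14.3%

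**Correlated outcomes, simulation.** No true effect, 26 per group, normal outcomes, 20,000 trials per setting. Each outcome has a Kruskal-Wallis test at 0.05; if it is significant, Mann-Whitney tests follow at 0.05/3.

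| Outcomes | Correlation | Any false omnibus result | Any false pair after the omnibus test |
|---|---|---|---|
| 1 | – | 5.0% | 3.9% |
| 2 | 0 | 9.4% | 7.6% |
| 2 | 0.5 | 8.6% | 7.0% |
| 2 | 0.7 | 8.4% | 6.9% |
| 3 | 0 | 13.7% | 11.0% |
| 3 | 0.5 | 12.6% | 10.1% |
| 3 | 0.7 | 11.3% | 9.2% |

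A separate run at correlation 0.8 gives 8.1% (two outcomes) and 10.2% (three) for the omnibus column. Over correlations 0 to 0.8 the ranges are therefore about 8% to 14% for the omnibus step and about 6% to 11% for the pairwise step.

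**The video claim alone.** Under the same two-step rule at correlation 0.5, a false video-versus-control result on any outcome occurs in 2.4% (two outcomes) and 3.7% (three). A second simulation gives 2.7% and 4.3%. Counting video against either other group raises this to 5.0% and 7.7%.

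**Power after the fix.** Omnibus ANOVA, f = 0.40, N = 78: 88.3% at 0.05 and 81.5% at 0.025.

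**The case against.** The strongest reply is that the study is about video, and the video-versus-control claim is already protected. The omnibus gate and the corrected pairs together hold it at about 2% to 4%, below 5%. This stands. A reader might infer from the omnibus rates that the headline video claim carries an error of 9% or more; the written two-step rule does not produce that.

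A reader might also count STAI-II as a fourth outcome and arrive at about 16%. Section 4 labels it a trait scale and gives it once, and no section calls it an effect outcome. The loose wording in section 11 is not enough to make it one.

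Three further points have weight:

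- The documents do not promise a 5% rate for the study as a whole, so no stated figure is broken.
- The Bonferroni family is not defined. If it spanned all pairs on all outcomes, the pairwise claims would be controlled, although the omnibus tests would still be uncorrected.
- Section 17 does put STAI first. Naming one STAI score as primary and calling pain supportive would hold the primary claim at 5%. The plan does neither: "statistical analysis of STAI responses before and after the procedure among different groups" covers more than one score and time point, and pain is in the title with no status.

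**Conclusion.** The concern holds in a limited form. The plan has no error control across its two STAI-I time points and post-biopsy VAS, and no single primary outcome that would make such control unnecessary. With two to three outcomes and correlations of 0 to 0.8, both assumed, at least one false omnibus result occurs in about 8% to 14% of null trials. At least one false pairwise claim after the omnibus test occurs in about 6% to 11%. The pairwise range also rests on reading Bonferroni as three pairs within an outcome.

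The documents do not support saying that a promised familywise rate is violated, or that the specific video-versus-control comparison is inflated above 5%. The weakness lies in the set of claims the study could make across groups and outcomes. It should be corrected, and it does not undermine the design.

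**What to change.** In section 17 and the final Statistical Analysis section:

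1. Name one STAI-I score and time point as the single primary outcome, chosen before the data are seen, and test it among the three groups at 0.05.
2. Test post-biopsy VAS at 0.05 as confirmatory only if the primary test is significant.
3. Report the other STAI-I time point, STAI-II and the correlation and regression results as exploratory.
4. Keep Bonferroni within each outcome, and state that its family is the three group pairs.

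If pain and anxiety are meant to rank equally, replace step 2 with Holm on the two omnibus p-values (primary STAI-I and VAS): the smaller against 0.025 and, if that is significant, the larger against 0.05.

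The cost is a few sentences, with no new patients or measurements. The fixed order leaves the first test at the full 0.05. Under Holm, even the stricter step keeps about 81.5% power at f = 0.40 with 78 patients, above the 80% target. The downside is that a pain difference without a STAI-I difference becomes exploratory or, under Holm, needs p<0.025.
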